## 5.1 Efficacy Assessment of the proposed technology

To get a reliable reference for confirming the presence of AF, we opted to use the Zio XT® ECG Patch (iRhythm Technologies, San Francisco, CA) in our project. iRhythm developed a patch sensor to record one-lead surface ECG continuously for a period of ~14 days. A growing number of studies demonstrated the effectiveness of this device in monitoring patient for AF burden. After the recording period is completed, the patch is mailed to iRhythm for semi-automatic analysis using the ZEUS system (Zio ECG Analysis Services) that combines cloud-based technology and cardiac technician review. In this work, we need to access the raw ECG signal in order to manually adjudicate the ECG rhythm and reliably define the onset and offset of AF episodes across the 14 days. We contacted iRhythm, and arranged that this company share the full raw ECG signals from their patch with our institution to conduct the proposed research work (see letter of support from iRhythm technologies, Zio unit price is ~\$260). The 14-day recordings will be cut into 14 signals of 24-hour length and reviewed using standard Holter approach (Global Instrumentation M12A Holter scanning system that utilizes input ECG waveform data in the ISHNE format). These recordings will then be manually adjudicated utilizing the THEW Viewer/Annotator technology developed in our laboratory for 24-hour ECG review (technology used daily in the THEW initiative). Importantly, we will define a clinically-relevant AF episode as a continuously-recorded AF rhythm lasting for a minimum of 5 minutes. Bringing monitoring technologies into the home introduces a series of technical and logistical challenges we discuss in the following sections:

Ensuring usability of the monitoring devices and high quality of recorded data are crucial to the success of this project:

- *Zio XT® ECG patch:* the usability of the patch and the quality of the ECG recording are of no concern in our study because this device is already a fully validated clinical device. From a logistic point of view, the subject will start wearing the patch before s/he leaves the hospital. The patch is placed on the flattest part of the upper left chest, its location is defined using 1 finger width below the collarbone, centered over the left pectoral muscle with the edge of the ZIO Patch next to the sternum, and with an angle so that the arrow on the top patch label points upward. It is important to avoid armpit and breast tissue. There is no activity restriction when the subject wears the ECG patch. The subject will receive a package to mail both the tablet and the patch at the end of the monitoring period (14 days) to the ECG Core Laboratory (ECL) of the Heart Research Follow-up Program. The ECL will 1) load the VPG data from the tablet for processing and 2) will mail the patch to iRhythm for analysis and ECG signal extraction. This data will be available electronically to the ECL using a secured BOX™ server (cloud technology already used by the HRFUP in several FDA-regulated clinical trials).
- *The iPad and Samsung TAB III tablet:* the tablet will provide the following functionalities: 1) VPG monitoring during the time the tablet is used, and 2) a symptom reporting APP that needs to be triggered by the subject if he/she feels AF symptoms, and 3) a Notification APP that will be automatically triggered to insure subject compliance to the protocol.
  - VPG monitoring:

The tablet will automatically acquire the facial video of the subject when it is in use. Subjects will be asked to utilize the tablet a minimum of 5 minutes, twice a day (in addition to scheduled and symptomatic recordings). The tablet will record successive 30 sec. facial video recordings, extract the information from the video, and send the data to a secured cloud-server (BOX.com). A single picture of the face of the subject will be extracted from the video (at the beginning of each 30sec. recording). This image will be encrypted and sent with the

pulsatile data to the cloud server. Video will then be deleted from the device's hard drive. Subjects will also be required to perform a VPG of his/her face and finger twice daily (with 6 hours between VPGs). The recording of the subject's finger uses the Tablet's flashlight feature through the camera lens on the back of the Tablet to obtain pulse information via the light passing around and through their index finger, and involves little or no risk. The procedure is similar to standard finger pulse oximetry used in hospitals as well in personal use with new wearable devices for measuring oxygen saturation levels and pulse.

- Symptoms APP: Common symptoms often associated with AF are reviewed with the subject by the study nurse as part of the subject's enrollment process and training.

When the subject feels any of these AF symptoms, she/he will run the SYMPTOMS APP on the tablet that will require the user to respond to the following questions related to AF symptoms:

**SELECT SYMPTOMS THAT YOU ARE CURRENTLY EXPERIENCING:**

- Palpitations (feeling that your heart is skipping a beat, fluttering, or beating too hard or fast)
- Shortness of Breath
- Chest Pain
- Dizziness, Fainting (loss of consciousness)
- Confusion
- Fatigue (tiredness)
- Sporadic Flushing In the Face
- Feelings of fear or anxiousness.

After entering the responses, the subject presses the application's Submit Button and, if the subject selected any of the first five symptoms, the following "seek medical attention recommendation" will appear:

**"You have noted that you are experiencing one or more of the major symptoms listed. It is recommended that you call your doctor or seek other medical attention to help relieve your symptoms and possibly prevent further medical complications."**

The subject then must perform two recording sessions of 30sec each. First, a facial VPG followed by a finger VPG recording.

- Notification APP: This APP will run in the background and monitor whether a subject has performed the twice per day VPG of his/her face and finger. To insure that the subject has performed the twice per day VPG recordings, the tablet's Notification APP will notify the subjects up to four times a day (8am, 12pm, 4pm, & 8pm) that a recording is needed to comply to the twice per day recording protocol. If the subject has not performed the task, the APP will provide a verbal message informing the subject that the recordings should be done and to: "Please select OK to take a video". If the subject selects "OK", then the Tablet provides additional verbal instructions on taking the videos and synchronize them with the ECG Patch recording.

When the facial video is completed, the system will then inform the subject that the facial video is done, and that a video of the subject's finger is to be performed by a light shining through the camera lens located on the back of the Tablet:

**"Thank you, your facial video is done."**

**"Please use the camera lens on the back of the Tablet to now perform a video of your index finger. Please do not remove your finger until the light goes out."**

The subject will then turn the tablet over and place his/her index finger on the camera lens located on the back of the Tablet, and a light will turn on and shine on the subject's finger. The subject will be required to let his/her finger remain in that position until the light goes out.

When the video is completed the Tablet will go back to the previous screen in use by the subject.

The Notification APP will continue to run in the background and perform its notification process (as described above). The APP will notify the subject up to four times a day (8am, 12pm, 4pm, & 8pm) that a video recording should be done.

The tablets will be setup so the user cannot download and install novel applications that may interfere with the VPG program or/and critically reduce the storage space of the device. Compliancy of the subject with the study protocol will be verified by checking the flow of data onto the cloud server by study staff on a daily basis. Video quality will be qualified using facial detection and other metrics that measure the level of motion of the face in terms of horizontal and vertical axes (expressed in pixels) and analysis of power spectrum. A study research staff member will contact the subject when less than 2 recordings are recorded and sent to the cloud server on a daily basis (we will exclude recordings done by other individuals using the device). A correction plan will be developed on a case-by-case basis. Subjects not having internet home access will not be enrolled in the study.

**Subject training:** The patients will be contacted by phone and asked to be enrolled in the study prior to their admission to the hospital. When enrolled, and while waiting (45-60 minutes) for their procedure in a private exam room, a research staff member will spend ~ 30 minutes with the subject before their procedure: 1) to describe how to use the personal computer and the embedded applications for the video recordings; 2) to teach the subject to recognize a set of AF symptoms that should alert him/her to record additional VPGs; and 3) to provide contact information for technical support (by the Project IT Manager) in case subject has difficulty using the device. The tablet will also be loaded with training videos/materials available from the tablet's start screen. The subjects will be taught to recognize the AF symptoms (described above) and will be asked to record a facial and finger VPG during those symptoms. A study website (containing the training materials and videos) is available only for subject use through the THEW main website at <http://thew-project.org/camafib/index.php>.

At the end of the 14-day period, the subject is asked to remove the ECG patch using the procedure described during enrolment (also a video demonstrating the procedure will be available on the tablet). Insert the patch with the Tablet in the provided box, and mail the box to the ECG Core Laboratory (ECL) at the Heart Research Follow-up program.

## 5.2 Cost to the Subject

There will be no cost to subject for their participation in this study.

## 5.3 Payment for Participation

Finally, as an incentive for patients to enroll in the study, we will offer the subjects who complete the 14-day follow-up period a payment of \$100 (per check mailed to their home address). If a subject withdraws from the study, no study incentive will be paid.

## 5.4 Project Time Frame

We propose to conduct this project over 8 semesters (S1 to S8) from 2/1/2017 to 1/30/2021. The timeframe will be as follows: study setup, software integration to tablets (S1); subject enrollment for the learning (S2-S4) and validation (S5-S7) datasets; refinement of the AF detection method (S3-S7); validation and publications (S8).

|                                     | Timeframe (months) | S1 | S2 | S3 | S4 | S5 | S6 | S7 | S8 |
|-------------------------------------|--------------------|----|----|----|----|----|----|----|----|
| Study setup                  | 6                  |    |    |    |    |    |    |    |    |
| Enrollment (learning set)    | 17.5               |    |    |    |    |    |    |    |    |
| Enrollment (validation set)  | 17.5               |    |    |    |    |    |    |    |    |
| Data quality monitoring      | 35                 |    |    |    |    |    |    |    |    |
| Develop AF detection method  | 30                 |    |    |    |    |    |    |    |    |
| Validate AF detection method | 3                  |    |    |    |    |    |    |    |    |
| Publications                 | 3                  |    |    |    |    |    |    |    |    |

Table 3: Time frame of the proposed project over a period of 4 years (8 semesters: S1 to S8).

## **6. RISK/BENEFITS:**

This is a minimal risk study. The ZIO® XT Patch could cause irritation such as redness, severe itching or allergic symptoms (i.e. hives). Identifiable facial images could result in a breach of confidentiality (addressed above). If skin irritation such as severe redness, itching or allergic symptoms develop and persist during the recording period, the subject should remove the ECG patch from their chest and contact the Study Staff (that attached the patch) for any additional instructions/support. The subject will also be encouraged to subsequently advise their primary Care physician that they may have an allergic reaction to medical adhesives. If significant skin irritation persists or if the subject's skin has blistered, they will be advised to seek medical treatment. There is no direct benefit to subjects for their participation. The ECG's will be reviewed by an ECG expert or cardiologist during the following month and the subject will be contacted by [name] or a member of the study team if the results indicate further follow-up is needed.

## **7. CONFIDENTIALITY OF DATA AND INFORMATION STORAGE:**

We have planned to acquire and analyze one-lead electrocardiograms and video-recordings of subjects' face and finger. The ECG recordings will be associated with subject ID and fully de-identified. There is a potential for data loss/hacking for the facial images going through the web. Although this potential is minimal, we have imposed the following processes to protect the data: The video recordings will be deleted automatically from the tablet after processing and one single image of the face will be kept and associated with the recording measurement. These two pieces of information will be gathered in a single encrypted file. This file will be stored on the tablet and transmitted to a cloud server (BOX.com) using encryption schemes. Therefore, the data recorded with the Tablet are encrypted and moved and stored using devices that are password-protected in order to secure the subject privacy. Data access will be granted only to the individuals involved in the project. The HIPAA requirements around the video data were already addressed when we designed and conducted the study described in the preliminary results. The requirements include specific enrollment and consent forms that describe precisely to the patients how their data will be used, and which organizations will have access to them for research purpose.

Data will be stored in a secure server at the University of Rochester with access limited to study personnel. The cloud server used to host the 30-sec recordings is a Box.com server that is password protected.

Importantly, the facial video images will not be shared with the other organizations (outside of the URMC) in this study in order to protect the privacy of the study subjects. Signals without personally identifying information (VPG only) will be shared with the study collaborators (RIT). All data will be de-identified by URMC to comply with the HIPAA "Safe Harbor" method of de-identification set forth at 45 CFR 164.514(b) prior to disclosure to RIT's investigator. Signed consent forms will be stored in a locked file cabinet with access limited to study personnel. Data will be stored indefinitely.

## **8. DATA ANALYSIS AND MONITORING**

### **8.1 Power and Sample Size Considerations**

In absence of good information on the dependence between the binary AF outcomes over time, we will very conservatively base our power calculations on just one measurement per patient. It is expected that about 35% of patients will experience at least one episode of symptomatic AF within the 2-week follow-up period, while we also expect to capture the occasional asymptomatic AF with the twice daily monitoring. We will thus assume that 35-65% of patients will be in AF at some point during follow-up. Thus of the 142 patients in the Validation Data, we expect 50-92 (but closer to 50) patients to contribute to the estimate of sensitivity, and similarly 50-92 (but closer to 92) patients to contribute to the estimate of specificity. Assuming the true sensitivity (and specificity) is 85%, 50-92 patients in AF provide 75-96% power to reject the null hypothesis that sensitivity  $\leq$

70% using a 1-sided 0.05 level exact binomial test, and similarly for specificity. The power for our planned test based on not just one but all 29 measures for each patient will be higher, especially for testing specificity since the proportion of the 4K measurement times in AF will likely be far less than the proportion of the 142 subjects ever in AF.

## **8.2 Implementation of the Learning and Validation steps**

It is important to note that during the Validation phase of the project, [name] PhD, MBA will be excluded from evaluating the performance of the VPG technology because of the potential for a conflict of interest. His role during this phase of the project will be that of a technical consultant only. In addition, for the validation phase, blinded study data will be sent to RIT for processing and the results will be sent to [name] (U of R) for evaluating the performance of the tested technology to detect the presence of AF. [name], Department of Biostatistics, will be responsible for the statistical analysis of the clinical data at the UR.

**-AIM1, Detection Performance of VPG:** To address Aim 1 we will use the Training Data) to construct a classifier to predict AF as a function of facial VPG measures, then we will use the Validation Data to provide an unbiased characterization of its performance on independent subjects. Each subject will record a baseline VPG during sinus rhythm. During the 2-week follow-up period, subjects will be asked to record a video selfie (VPG) twice per day, each synchronized with the ECG recording from the Zio patch. Subjects will be asked to perform additional VPG recordings any time they feel symptomatic. The longitudinal binary outcome at each follow-up time will be AF as determined by ECG. We expect to have a minimum of 29 outcomes per patient (2 weeks x 7 days/week x 2 recordings/day + 1 baseline) x 142 patients (half of the 315 enrolled x 90% converted) = 4K outcomes in the Training Data (and similarly in the Validation Data), each with an associated VPG from which the 8 VPG measures described above (PR, heart rate, RMSSD, SDRR, pNN50, SD1, SD2, AFEvidence) will be calculated.

A working independence-based logistic GEE (Generalized Estimating Equations) model will be used to construct the classifier, essentially ignoring any potential dependencies between the longitudinal AF outcomes. We will relax the common assumption of linearity in the logit by considering piecewise constant (or piecewise linear) splines with knots at the quartiles (or tertiles) of each VPG measure, resulting in 3 candidate basis functions per VPG measure (for a total of 24 candidate VPG basis functions). All-subsets and stepwise model selection procedures will be used to select a subset of the VPG basis functions, though the indicator for subject type will be included in all models. Five-fold cross-validation (at the subject level, each time omitting all observations on 28 of the 142 Training subjects to maintain independence) may be used to help select the nominal significance level, or model size, as well as the threshold necessary to form the logistic classifier. We will consider relaxing the assumption of additivity by further allowing 2-way interactions between pairs of nominally significant VPG measures.

Once we have selected the VPG measures, their functional forms, any interactions, and a threshold for the resulting linear predictor –as well as completed the Training phase for Aim 2 (as noted below)– all using only the Training Data, we will finally use the independent Validation Data to characterize the performance of the resulting classifier, free of model selection bias. Sensitivity and specificity will be empirically estimated by the marginal mean of the indicators, weighting each of the 4K observations equally, with inference based on robust sandwich covariance estimators accounting for potential dependencies between the multiple outcome measures from each subject. Alternatively, we will first compute subject-specific estimates of sensitivity and specificity, and then average these over independent subjects, thus weighting each subject (rather than each measurement) equally. We will construct robust 90% two-sided confidence intervals (CI) for the sensitivity and specificity, since we are primarily interested in the 95% lower confidence bounds. Although hypothesis tests are of less interest than the point estimates and CI, since the choice of null hypothesis is somewhat arbitrary here, we plan to test the alternatives that sensitivity >70% and specificity >70% (hoping for at least 85%), using 1-sided 0.05 level tests for each. Thus, e.g. if the 90% two-sided CI for sensitivity is fully contained with 0.7-1.0, we will reject the null hypothesis that sensitivity  $\leq$  70% at the 0.05 level.

We will also construct ROC curves based on the Validation Data to display the trade-off between sensitivity and specificity as a function of the threshold for the linear predictor, and we will compare these to cross-validation-based (as well as optimistic naïve) ROC curves based on the Training Data. To investigate calibration, we will fit a marginal logistic model to the Validation Data with the un-thresholded linear predictor as the sole predictor. Testing the null hypothesis that the slope in this model is 0 tests whether the model is useless, and thus we hope and expect to strongly reject this null hypothesis with a tiny p-value; testing the null hypothesis that the slope is 1 is a test of calibration, and we hope that we fail to reject this null hypothesis with a large p-value (indicating good calibration). We will also use the Validation Data to re-estimate all of the individual coefficients in the marginal logistic regression model, for comparison with the potentially biased estimates from the Training Data.

**-AIM2: Benefit of using Baseline VPG Recording:** Each subject will have a baseline VPG recorded during sinus rhythm (using the Samsung Tablet). This recording will be acquired after successful procedure and before the subject leaves the hospital. Sinus rhythm will be checked by health professional. To address Aim 2, we will repeat the above general procedure but based on the *differences* from baseline in VPG measures and/or by including the baseline VPG measures along with the instantaneous VPG measures for predicting AF at each time point. When the time comes to open the Validation Data, we will compare the sensitivity and specificity of the classifier from Aim 2 to that of Aim 1 to quantify the potential improvement due to incorporating a baseline VPG.

[figure not shown]

Figure 7: Schematic presentation illustrating the true and false detection of AF and SR rhythm during the 14-day follow-up period of the study. The upper line represents the continuous ECG recording (either blue or black for SR and AF, respectively), while the lower line presents the same 14-day period during which VPG will be recorded. The VPG monitoring periods in which 5 recording sessions are marked (limited to 5 for clarity purpose). We will have at least 2 recording sessions per day, i.e., 28 recordings sessions.

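### The in-hospital sinus-rhythm baseline is scored as one of 29 outcomes per patient; on differences from baseline this gives Aim 2 a small built-in specificity advantage over Aim 1.

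*Combined protocol and SAP*

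**What the plan says.** Section 8.2 (Aim 1) sets the number of scored outcomes: "We expect to have a minimum of 29 outcomes per patient (2 weeks x 7 days/week x 2 recordings/day + 1 baseline". Multiplied by 142 patients, this is given as about 4K outcomes in the Training Data, and similarly in the Validation Data. Section 8.1 ties the planned test to the same count, describing it as "based on not just one but all 29 measures for each patient". The same Aim 1 text also says "The longitudinal binary outcome at each follow-up time will be AF as determined by ECG", which on its own would suggest follow-up recordings only.

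Two specificity estimators are offered. One pools recordings, "weighting each of the 4K observations equally". The other averages patient-level estimates, "thus weighting each subject (rather than each measurement) equally".

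On the baseline itself, the Aim 2 text says: "This recording will be acquired after successful procedure and before the subject leaves the hospital". Sinus rhythm is confirmed by a health professional. Aim 2 repeats the Aim 1 procedure on differences "from baseline in VPG measures and/or by including the baseline VPG measures along with the instantaneous VPG measures", then compares sensitivity and specificity with Aim 1 on the Validation Data. It gives no row count of its own and does not say that the baseline row is dropped. Aim 3 starts its false-detection clock at hospital discharge.

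**The concern.** The primary aim (section 1.3) is detection at home with a tablet the patient operates. The baseline is recorded in hospital and is in sinus rhythm by design, so it can count only towards specificity.

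For Aim 1 this means that a few percent of the scored rows are not home recordings; no bias is shown. The consequence that matters is in Aim 2. If the same rows are used, each patient's baseline is compared with itself and is zero on all eight VPG differences. The only other forced term is patient type ("the indicator for subject type will be included in all models"). In a differences-only model, all baseline rows of one patient type therefore get the same score. Since 142 training rows, all non-AF, sit at that point, a correct call is almost certain.

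The artefact falls on the quantity Aim 2 exists to estimate, namely what the baseline adds. No test or margin is stated for the comparison, so a small artificial gain could be read as improvement.

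**Working it through.** **Inputs.** From the documents: 28 scheduled follow-up recordings plus 1 baseline; 142 patients per dataset; hoped-for specificity 85% and null value 70%; 95 of 284 converted patients with early recurrence (Table 1); recurrence at a mean of 3.7 days, SD 3.5, in one post-ablation cohort (section 3.1). The share of home recordings in AF, f, is not given, so it is assumed and shown as a range.

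**The plan's count.** 315 x 0.90 / 2 = 141.75, or 142. Then 29 x 142 = 4,118, which matches the stated 4K. Without the baseline, 28 x 142 = 3,976, which also rounds to 4K. The total therefore does not settle whether the baseline is scored; the explicit 29 does. The 28 sessions in the Figure 7 caption are consistent with 28 follow-up + 1 baseline. The baseline is 142/4,118 = 3.4% of rows.

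**Size of the advantage.** Suppose Aim 1 classifies baseline rows as well as home rows (specificity Sp) and Aim 2 classifies them all correctly. Then:

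gain = (baseline share of sinus-rhythm rows) x (1 - Sp).

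*Pooled weighting.* Share = 142 / (142 + 3,976(1 - f)).

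| f (assumed) | share | gain at 85% | gain at 70% |
|---|---|---|---|
| 5% | 3.62% | 0.54 points | 1.09 points |
| 10% | 3.82% | 0.57 | 1.15 |
| 20% | 4.27% | 0.64 | 1.28 |
| 30% | 4.85% | 0.73 | 1.46 |

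One scenario uses the documents' recurrence figures. 95/284 = 33.5% recur. Onset at day 3.7 leaves 3.7 x 2 = 7.4, or 7 sinus-rhythm recordings. If AF then persists to day 14 (an assumption), f = 0.335 x (1 - 7/28) = 25.1%. The share is 4.55% and the gain 0.68 points at 85%, 1.37 at 70%.

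*Subject weighting.* With n sinus-rhythm follow-up recordings, the baseline is 1/(n + 1) of a patient's specificity: 3.4% for n = 28, 12.5% for n = 7, 20% for n = 4 and 100% for n = 0. Mean share = 0.665/29 + 0.335 x mean of 1/(n + 1) in patients with recurrence.

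| Patients with recurrence | mean share | gain at 85% | gain at 70% |
|---|---|---|---|
| about 10% of recordings in AF (n = 25) | 3.58% | 0.54 points | 1.07 points |
| onset day 3.7, AF persists (n = 7) | 6.48% | 0.97 | 1.94 |
| gamma onset, mean 3.7, SD 3.5 days, cut at 14 days, AF persists | 11.9% | 1.78 | 3.57 |

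The last row rounds n down; rounding to nearest or up gives 1.5 or 1.3 points at 85%.

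**If Aim 1 does better on the baseline.** With Aim 1 specificity of 95% at baseline and 85% at home, the pooled gain is share x 0.05 = 0.18-0.24 points.

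**Simulation (illustrative, distributions assumed).** All eight measures were entered as quartile terms (24 basis functions) plus patient type, with no selection step and a differences-only Aim 2. About 7-26% of home rows were in AF; there were 12 scenarios of 50 runs. All Aim 2 baseline rows were called correctly in 98-100% of runs. At home specificity of about 84-85%, scoring the baseline inflated Aim 2 by 0.56-0.74 points pooled and 0.58-2.08 subject-weighted. Aim 1 pooled specificity moved by -0.06 to +0.02. In one setting of a simpler one-measure simulation the ranking reversed: on follow-up only, Aim 2 was at 83.2% against 83.7% for Aim 1; with the baseline scored, 84.0% against 83.7%.

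**The case against.** The strongest reply is that the biased implementation is inferred. The 29 is stated for Aim 1, within a rough projection. Aim 2 gives no row count, the outcome is defined at follow-up times, and an analyst working with changes from baseline may well drop a row that is zero by construction. That is possible, but the written rule scores the row, section 8.1 bases the test on all 29, and nothing removes it from Aim 2.

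Second, the argument applies in full only to the differences version. With baseline measures added as covariates, a sinus-rhythm call at baseline is not forced. This stands, and the figures above are for differences only.

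Third, the threshold rule is open. If the threshold were set to a fixed specificity on the same rows, part of the gain would move to sensitivity. That also stands, but it relocates the distortion without removing it.

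Fourth, the gain is small against sampling error. Assume 5-25% of recordings in AF. The 90% interval half-width for one specificity at 85% is then about 1.0-1.1 points with independent rows, and 1.8-2.9 with assumed within-patient correlation of 0.1-0.3. For the paired difference, with an assumed 10% of rows discordant, it is about 0.8-2.5 points. The pooled gain at 85% is below all of these. This supports a minor rating. The artefact nevertheless has a known direction and does not shrink with more patients.

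Fifth, the larger figures need persistent AF. The 3.7-day mean comes from an ablation cohort, whereas two-thirds of planned enrolment is cardioversion. Section 8.1 also expects the proportion of measurement times in AF to be far below the proportion of patients ever in AF. Those figures are upper scenarios.

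**Conclusion.** The concern holds and is minor. Followed as written, the plan scores a row that carries no information about home performance and credits it almost automatically to Aim 2 specificity. The pooled advantage is about 0.5-0.7 points at 85% specificity and 1.1-1.5 at 70%. With subject weighting at 85% it is about 0.5 points at low AF burden, 1.0 if all recurrences start at day 3.7 and persist, and up to 1.8 if onset also varies.

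These sizes rest on four assumptions: the same rows are used in both aims, Aim 2 is fitted on differences only, Aim 1 does no better on the baseline than at home, and AF burden lies in the assumed ranges. A cleaner supervised baseline recording, or covariate-only use, would shrink the effect.

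**What to change.** Use the baseline only as a reference or predictor in Aim 2. Score Aims 1 and 2, in training and in validation, on the same post-discharge recordings: the 28 scheduled ones plus any symptomatic ones. This matches Aim 3, which already starts at discharge. In sections 8.1 and 8.2 change 29 to 28 and delete the baseline term from the count; 28 x 142 = 3,976 is still about 4K. Baseline specificity can be reported separately if wanted. Make the change before the Validation Data are opened.

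The cost is a few wording edits and 142 of 4,118 rows (3.4%), none in AF. The pooled specificity standard error rises by sqrt[(28(1 - f) + 1) / (28(1 - f))] - 1, which is 1.9% at f = 5% and 2.5% at f = 30% in relative terms with independent rows. Patients with no sinus-rhythm recording after discharge leave the subject-weighted specificity, but they carry no information on home specificity. The trained threshold may shift slightly. The stated 75-96% power is unaffected because it uses one measurement per patient.
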